9.2 Data Collection

Table 1 shows the data collection requirements and Scheduled Visit Windows

Early Adapter Part II Study Clinical Investigation Plan

MDT20041

Version 6.0

Page 27 of 88

Form

Medtronic

Table 1: Data collection and study procedure requirements at subject visits

Visit	Enrollment	Baseline	Randomization	aDBS Treatment Phase					Follow-up phase			Exit
				Visit 1	Out of clinic	Visit 2	Out of clinic	Visit 3	Visit 4	Visit 5	Visit 6	
Visit ranges (From the previous visit)		Up to 30 days		Up to 30 days		45 days ⁴		45 days ⁴	45-60 days ⁴	45-60 days ⁴	45-60 days ⁴	
Informed Consent	X											
Demographics		X ¹										
Medical & surgical history		X ¹										
PD history		X ¹										
Device Information		X ¹										
MRI/ CT image data		X ¹										
Signal Test/LFP threshold setting		X ¹										
aDBS washout (7 days or more)		X										
Randomization			X									
Concomitant medications (non-PD)		X		X		X		X	X	X	X	
PD medication		X		X		X		X	X	X	X	
Program initiation (cDBS or aDBS)				X		X						
PDQ-39				X		X		X	X	X	X	
EQ-5D-5L				X		X		X	X	X	X	
UDysRS				X		X		X	X	X	X	
MDS-UPDRS II ("best" conditions)				X		X		X	X	X	X	
MDS-UPDRS II ("worst" conditions)				X		X		X	X	X	X	
MDS-UPDRS III				X		X		X	X	X	X	

Early Adapter Part II Study Clinical Investigation Plan

MDT20041

Version 6.0

Page 28 of 88

Form

Medtronic

Visit	Enrollment	Baseline	Randomization	aDBS Treatment Phase					Follow-up phase			Exit
				Visit 1	Out of clinic	Visit 2	Out of clinic	Visit 3	Visit 4	Visit 5	Visit 6	
Visit ranges (From the previous visit)		Up to 30 days		Up to 30 days		45 days ⁴		45 days ⁴	45-60 days ⁴	45-60 days ⁴	45-60 days ⁴	
MDS-UPDRS IV				X		X		X	X	X	X	
DBS GIC						X		X				
Preference questionnaire		X ¹						X ⁵				
Satisfaction questionnaire								X ⁶			X	
Apple Watch/iPhone distribution and programming				X								
Apple Watch/iPhone data collection**				X	X ²	X	X ²	X	X	X	X	
Device data		X ³		X		X		X	X	X	X	
Event markers (Option)					X		X		X	X	X	
Adverse Events	As they occur											
Device Deficiencies	As they occur											
Protocol Deviations	As they occur											
Reason for exit												X

¹ Not required if data collected prior to Early Adapter Part II

² PD Medication cycle, every 14 days during 45 days of Period A and B; Calendar reminders set on Apple Watch, with instructions

³ If Signal test was implemented

⁴ Visit ranges ± 7 days

⁵ Perform before unblinding subjects

⁶ Perform after unblinding subjects

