9.8.3. Post Period B/Visit3

45(±7) days after Post Period A/Visit2

The PI/ Sub investigator should confirm the subject is in the assigned mode for this visit. If the subject is not in the assigned mode, a deviation CRF will be completed and the reason for the mode change will be collected. If applicable the subject will start the visit over again after 45(±7) days, where possible, i.e. if the subject tolerates well the assigned mode and the assigned mode is setup if the subject was switched to another mode by accident.

The following data will be collected:

- Concomitant medications (non-PD)
- PD medications
- Programming session upload, with device interrogation and BrainSense data included in the

JSON session data report

- PDQ-39 (subject's assessment of prior 30-day period on the assigned mode in Period B)
- EQ-5D-5L
- MDS-UPDRS II ("best" conditions)
- MDS-UPDRS II ("worst" conditions)
- MDS-UPDRS III (On stim/On med) – trained rater
- MDS-UPDRS IV – trained rater
- UDysRS (subject's assessment of prior 30-day period on the assigned mode in Period B)
- DBS Global Impression of Change score (DBS GIC)
- Patient preference questionnaire: Perform the Patient preference questionnaire of the modes assigned to period A and period B before unblinding subjects
- Patient satisfaction questionnaire: Perform the Patient satisfaction questionnaire on aDBS after unblinding subjects
- Upload data collected from Apple Watch/iPhone, including movement and sleep data *,**
- Event markers (optional)*
- AE and device deficiency assessment (As they occur)
- Protocol Deviations (As they occur)

*: Confirm if it has been done

** : In principle, the data collected from an iPhone will be used for Data of PD medication cycle, but if the data is missing, the data recorded in a medication diary etc. can substitute.

Following the end of Post period B visit, the PI/ Sub investigator breaks the blinding of a subject. For the next follow-up visit, the PI/ Sub investigator should program the subject to preferred DBS mode (aDBS or cDBS), taking into account the study subject's medical condition.

If the preferred mode is cDBS, the subject will be exited from the study following the process in section 9.15. No further study-related procedures will be completed, and subjects will be followed according to the site's standard procedures.

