9.9.2. Visit5

45-60 (± 7) days after visit4

The subjects will arrive for the visit on subject's preferred aDBS mode.

The following data will be collected:

- Concomitant medications (non-PD)
- PD medications
- Programming session upload, with device interrogation and BrainSense data included in the JSON session data report
- PDQ-39 (subject's assessment of prior 30-day period on subject's preferred aDBS mode)
- EQ-5D-5L
- MDS-UPDRS II ("best" conditions)
- MDS-UPDRS II ("worst" conditions)
- MDS-UPDRS III (On stim/On med) - trained rater
- MDS-UPDRS IV – trained rater
- UDysRS (subject's assessment of prior 30-day period on subject's preferred aDBS mode)
- Upload data collected from Apple Watch including movement and sleep data *
- Event markers (optional)*
- AE and device deficiency assessment (As they occur)
- Protocol Deviations (As they occur)

*: Confirm if it has been done

For the next follow-up visit, the PI/ Sub investigator should program the subjects to preferred DBS mode (aDBS or cDBS), taking into account the study subject's medical condition.

If the preferred mode is cDBS , the subject will be exited from the study following the process in section 9.15. No further study-related procedures will be completed, and subjects will be followed according to the site's standard procedures.

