9.9.3. Visit6

45-60 (± 7) days after visit5

The subjects will arrive for the visit on subject's preferred aDBS mode.

The following data will be collected:

- Concomitant medications (non-PD)
- PD medications
- Programming session upload, with device interrogation and BrainSense data included in the JSON session data report
- PDQ-39 (subject's assessment of prior 30-day period on subject's preferred aDBS mode)
- EQ-5D-5L
- MDS-UPDRSII ("best" and "worst" conditions)
- MDS-UPDRS III (On stim/On med) - trained rater
- MDS-UPDRS IV – trained rater
- UDysRS (subject's assessment of prior 30-day period on subject's preferred aDBS mode)
- Patient satisfaction questionnaire
- Upload data collected from Apple Watch including movement and sleep data.*
- Event markers (optional)*
- AE and device deficiency assessment (As they occur)
- Protocol Deviations (As they occur)

*: Confirm if it has been done

At the completion of this visit, they will be exited from the study following the process in section 9.15.

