9.15.1. Study Exit

A study exit CRF is required for all subjects. Subjects are urged to remain in the study as long as possible but may be exited from the study for any of the following situations:

- Study completed
- Subject lost to follow-up
- Subject death
- Subject's DBS Therapy System permanently explanted (i.e., neurostimulator, lead, extension)

- Subject did not meet inclusion/exclusion criteria
- Subject chooses to withdraw (e.g., consent withdrawal, relocation to another geographic location)
- PI/ Sub investigator deems withdrawal necessary (e.g., medically justified, inclusion/exclusion criteria not met, failure of subject to maintain adequate study compliance)

The PI/ Sub investigator will attempt to collect the following information prior to the subject's early discontinuation from the study:

- Adverse event and device deficiency assessment
- Programming session report, with device interrogation and BrainSense data included in the JSON session data report upload
- A brief description of why the subject discontinued (if applicable)

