7.9.3.8 Patient Satisfaction

To assess Patient satisfaction with aDBS (preferred mode).

Endpoint definition

Patient satisfaction questionnaire

Analysis methods

The patient satisfaction questionnaire will assess the overall satisfaction and satisfaction on specific items on 5 levels of satisfaction (very satisfied, somewhat satisfied, neutral, somewhat unsatisfied and very unsatisfied) and by the recommendation of adaptive DBS to other DBS patients with Parkinson's Disease. The responses will be summarized as categorical measures only for aDBS mode (any preferred mode).

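### Visit 6 satisfaction with aDBS comes only from subjects kept on aDBS, because those returned to cDBS at Visit 4 or 5 are not asked again

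*Protocol*

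**What the plan says.** **Exit rule.** At the close of Visit 3 (CIP 9.8.3) the investigator is to "program the subject to preferred DBS mode (aDBS or cDBS), taking into account the study subject's medical condition". The section goes on: "If the preferred mode is cDBS, the subject will be exited from the study following the process in section 9.15". It then adds: "No further study-related procedures will be completed, and subjects will be followed according to the site's standard procedures". CIP 9.9.1 (Visit 4) has the same rule, and so does 9.9.2 (Visit 5): "the subject will be exited from the study following the process in section 9.15". Those still in the study at the end are on aDBS; 9.9.3 says of Visit 6: "The subjects will arrive for the visit on subject's preferred aDBS mode".

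**When satisfaction is asked.** Table 1 in CIP 9.2 schedules the satisfaction questionnaire at Visit 3 (footnote: "Perform after unblinding subjects") and at Visit 6. The Visit 4 and Visit 5 lists do not contain it. They do contain PDQ-39, EQ-5D-5L, MDS-UPDRS II to IV, UDysRS and device data.

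**What is recorded at exit.** CIP 9.15.1 says subjects "may be exited from the study for any of the following situations" and lists them; return to cDBS by preference is not on the list. Before an early exit the site tries to obtain adverse events and device deficiencies, a device data upload and a short reason.

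**Analysis.** SAP 7.9.3.8 says only: "The responses will be summarized as categorical measures only for aDBS mode (any preferred mode". It names no visit, no denominator and no handling of subjects who exited. SAP 7.9.3 assigns the additional objectives to the Complete Case set, and SAP 7.4 rules out imputation.

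**The concern.** Patient satisfaction with aDBS is a listed additional objective in both documents, and Visit 6 is its only reading after longer use. Remaining in follow-up depends on the preferred mode, and preference is closely tied to satisfaction. If subjects who do less well on aDBS tend to be returned to cDBS at Visit 4 or 5, their later opinion is never collected, and the Visit 6 percentage is calculated among those who did better. A reader could then not tell lasting satisfaction from the departure of people who did not prefer aDBS. With about 20 subjects, a few departures are enough to move the figure visibly.

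**Working it through.** **1. Order of events at each visit (CIP 9.2, 9.8.3, 9.9.1 to 9.9.3)**

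| Visit | Satisfaction asked | Clinical scores taken | Mode decision and possible exit afterwards |
|---|---|---|---|
| 3 | yes | yes | yes |
| 4 | no | yes | yes |
| 5 | no | yes | yes |
| 6 | yes | yes | no, planned end |

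By time of exit:
- *Exit at Visit 3:* satisfaction has been scheduled at that visit; the subject has no follow-up phase.
- *Exit at Visit 4 or 5:* clinical scores exist for that visit, but the last satisfaction rating is from Visit 3. Follow-up visits are 45 to 60 days apart, so, leaving aside the ±7-day windows, the unrated aDBS use since Visit 3 is 45 to 60 days (exit at Visit 4) or 2 × 45 = 90 to 2 × 60 = 120 days (exit at Visit 5).
- *No exit:* second rating at Visit 6.

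**2. Does the analysis repair this?** Complete cases without imputation drop anyone with no Visit 6 rating from a Visit 6 summary. SAP 7.1.1 plans a CONSORT flow and a summary of attrition. That would show that subjects left, but it does not alter the satisfaction figure.

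**3. Size.** The documents give no expected share returning to cDBS, so there is no planned figure to reproduce on this point. The stated power concerns TEED: a difference of 22 and SD of 28 (effect size 22/28 = 0.79) with 20 subjects gives 91.5% at two-sided 0.05, in line with the stated 90% or more. It does not depend on follow-up. Every rate below is an assumption.

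*Retention.* If 20 finish the crossover and a share q exits for cDBS at each of Visits 3, 4 and 5, the number at Visit 6 is 20 × (1 − q)³: 17.1 for q = 5%, 14.6 for 10%, 10.2 for 20%.

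*Satisfaction.* Let p be the share of those entering follow-up who reach Visit 6, s₁ the satisfied share among them and s₀ the satisfied share among leavers. The Visit 6 figure is s₁; the figure for everyone is p·s₁ + (1 − p)·s₀. The inflation is (1 − p)(s₁ − s₀).

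| p | s₁ = 90%, s₀ = 30% | s₁ = 90%, s₀ = 50% |
|---|---|---|
| 90% | 6 points | 4 points |
| 80% | 12 points | 8 points |
| 70% | 18 points | 12 points |

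*Bounds from counts, 20 entering follow-up.*
- 18 reach Visit 6 and 16 are satisfied: 16/18 = 89%. Counting leavers as all unsatisfied or all satisfied gives 16/20 = 80% to 18/20 = 90%.
- 15 reach Visit 6 and 13 are satisfied: 13/15 = 87%. The range is 13/20 = 65% to 18/20 = 90%.

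*Clinical scores at visits after an exit.* If preference and outcome are jointly normal with correlation ρ and the top share p is retained, the mean among those retained shifts by ρ·φ(c)/p SD, where c = Φ⁻¹(1 − p). For p = 90%, 80%, 70% and 50% this gives 0.06, 0.10, 0.15 and 0.24 SD at ρ = 0.3, and 0.10, 0.17, 0.25 and 0.40 SD at ρ = 0.5. The shift is toward a better score. On PDQ-39 and MDS-UPDRS, where higher is worse (SAP 7.9.3.2 and 7.9.3.4), that means a lower score.

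**The case against.** The strongest reply is that follow-up is openly designed as visits on aDBS, is uncontrolled and is reported descriptively. Conditioning on aDBS is therefore a declared feature. Departures will be visible in the CONSORT flow, and an exit form with a reason is required for every subject. This stands as far as it goes. It makes the matter one of measurement and labelling, but it does not supply the missing rating or adjust the Visit 6 percentage.

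Other parts of the reply rule out stronger readings that a reader might infer:

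- *That dissatisfied subjects leave before each assessment.* The visit lists do not support this. At Visits 4 and 5 the full clinical battery comes before the mode decision. Only satisfaction, and clinical scores at later visits, are lost.
- *That every bias must favour aDBS.* The investigator also weighs medical condition when setting the mode, so selection is not on satisfaction alone. The direction is expected, most clearly for satisfaction, but it is not guaranteed, especially for rater-scored scales.
- *That Visit 6 EQ-5D-5L is a planned result that will be inflated.* SAP 7.9.3.1 ties that endpoint to Visits 2 and 3.
- *That a return to cDBS will be filed under the wrong reason.* The case report form is provided separately, so its codes cannot be seen. CIP 9.15.1 shows only that the protocol list lacks the entry.
- *That leavers should simply be scored as not satisfied.* That is a single-value imputation. It conflicts with the no-imputation rule in SAP 7.4 and could misclassify subjects moved for medical reasons.

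Finally, SAP 7.9.3.8 names no denominator. A responder-only Visit 6 percentage is the natural consequence of complete cases without imputation, not something the SAP states outright.

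**Conclusion.** The point holds in a limited form. Subjects returned to cDBS at Visit 4 or 5 give no satisfaction rating after longer aDBS use, and the Visit 6 result comes only from subjects kept on aDBS. Nothing in the SAP corrects or labels this. Follow-up clinical scores are affected at visits after an exit, not at the exit visit itself.

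The expected direction favours aDBS, on the assumption that preference and satisfaction are positively related. The size is unknown. The 6 to 18 points rest on assumed satisfaction of 90% and 30% and on 70% to 90% retention. The effect is nil if nobody exits or if preference is unrelated to the outcome.

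A reader might infer that the trial's main conclusion is at risk. It is not. The TEED and beta-LFP tests use the crossover periods, before the exit rule acts, and CIP 12.2 says they are not updated for the final report. The randomised aDBS versus cDBS comparison and Visit 3 satisfaction are also untouched. The change is worth making because it is cheap and concerns a listed objective.

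**What to change.** Leave the exit rule as it is, and:

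1. **CIP 9.9.1, 9.9.2 and Table 1:** give the existing satisfaction questionnaire at Visit 4 or 5 to any subject exiting because cDBS is preferred.
2. **Exit form and CIP 9.15.1:** make sure that return to cDBS is recorded as a distinct reason.
3. **SAP 7.9.3.8:** report the number and percentage still on aDBS at Visits 3 to 6, out of all randomised. Beside the Visit 6 responder-only figure, report the last available rating (Visit 6 or exit visit) for all who entered follow-up, and state how many have neither. These are observed ratings, so the no-imputation rule is kept. Count leavers as not satisfied only as a labelled lower bound.
4. **Follow-up tables:** label Visit 4 to 6 results *subjects remaining on aDBS*. Show beside them the same subjects' values from their aDBS period in the crossover (Visit 2 or Visit 3, according to sequence).

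Cost: one short questionnaire at a visit that already takes place, a check of one exit code, and SAP wording. The satisfaction figure may turn out less favourable.

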9.9 Follow-up Phase

Once subjects complete the aDBS treatment Phase, they enter a Follow-up Phase.

9.9.1. Visit4

45-60 (± 7) days after Post Period B /Visit3

The subject will arrive for the visit on subject's preferred aDBS mode.

The following data will be collected:

- Concomitant medications (non-PD)
- PD medications
- Programming session upload, with device interrogation and BrainSense data included in the JSON session data report
- PDQ-39 (subject's assessment of prior 30-day period on subject's preferred aDBS mode)
- EQ-5D-5L
- MDS-UPDRS II ("best" conditions)
- MDS-UPDRS II ("worst" conditions)
- MDS-UPDRS III (On stim)/On med) - trained rater
- MDS-UPDRS IV – trained rater
- UDysRS (subject's assessment of prior 30-day period on subject's preferred aDBS mode)
- Upload data collected from Apple Watch, including movement and sleep data*
- Event markers (optional)*
- AE and device deficiency assessment (As they occur)
- Protocol Deviations (As they occur)

*: Confirm if it has been done

For the next follow-up visit, the PI/ Sub investigator should program the subject to preferred DBS mode (aDBS or cDBS), taking into account the study subject's medical condition.

If the preferred mode is cDBS, the subject will be exited from the study following the process in section 9.15. No further study-related procedures will be completed, and subjects will be followed according to the site's standard procedures.

9.9.2. Visit5

45-60 (± 7) days after visit4

The subjects will arrive for the visit on subject's preferred aDBS mode.

The following data will be collected:

- Concomitant medications (non-PD)
- PD medications
- Programming session upload, with device interrogation and BrainSense data included in the JSON session data report
- PDQ-39 (subject's assessment of prior 30-day period on subject's preferred aDBS mode)
- EQ-5D-5L
- MDS-UPDRS II ("best" conditions)
- MDS-UPDRS II ("worst" conditions)
- MDS-UPDRS III (On stim/On med) - trained rater
- MDS-UPDRS IV – trained rater
- UDysRS (subject's assessment of prior 30-day period on subject's preferred aDBS mode)
- Upload data collected from Apple Watch including movement and sleep data *
- Event markers (optional)*
- AE and device deficiency assessment (As they occur)
- Protocol Deviations (As they occur)

*: Confirm if it has been done

For the next follow-up visit, the PI/ Sub investigator should program the subjects to preferred DBS mode (aDBS or cDBS), taking into account the study subject's medical condition.

If the preferred mode is cDBS , the subject will be exited from the study following the process in section 9.15. No further study-related procedures will be completed, and subjects will be followed according to the site's standard procedures.

9.9.3. Visit6

45-60 (± 7) days after visit5

The subjects will arrive for the visit on subject's preferred aDBS mode.

The following data will be collected:

- Concomitant medications (non-PD)
- PD medications
- Programming session upload, with device interrogation and BrainSense data included in the JSON session data report
- PDQ-39 (subject's assessment of prior 30-day period on subject's preferred aDBS mode)
- EQ-5D-5L
- MDS-UPDRSII ("best" and "worst" conditions)
- MDS-UPDRS III (On stim/On med) - trained rater
- MDS-UPDRS IV – trained rater
- UDysRS (subject's assessment of prior 30-day period on subject's preferred aDBS mode)
- Patient satisfaction questionnaire
- Upload data collected from Apple Watch including movement and sleep data.*
- Event markers (optional)*
- AE and device deficiency assessment (As they occur)
- Protocol Deviations (As they occur)

*: Confirm if it has been done

At the completion of this visit, they will be exited from the study following the process in section 9.15.

9.10 Unscheduled Visits

Any time the subject is seen for DBS programming adjustment or for an Adverse Event, the following data will be collected:

- Reason for the visit
- Concomitant medications (non-PD)
- PD medication: if applicable, PD medication and dose given at visit. Time of last dose of PD medications taken prior to the visit
- Programming session upload, with device interrogation and BrainSense data included in the JSON session data report
- Upload data collected from Apple Watch, including movement and sleep data*
- Event markers (optional) *
- Adverse Event and device deficiency assessment (As they occur)

*: Confirm if it has been done

9.11 System Modification

System modifications made to the DBS System will be completed according to the site's standard procedures. If the system modification occurs, the subject should be exited as needed, prior to receiving the system modification and considered for re-enrollment if possible. . Any visits for DBS setup due to a system modification will be recorded as unscheduled visits. If DBS cannot be acceptably set up, the subject will be exited from the study following the process in section 9.15.

Data collection:

- Device information (if applicable)
- Concomitant medications (non-PD)
- PD medication at visit: if applicable, PD medication and dose given at visit. Time of last dose of PD medications taken prior to the visit
- Programming session upload, with device interrogation and BrainSense data included in the JSON session data report

- Adverse Event and Device deficiency assessment (As they occur)

9.12 Assessment of Safety

AE information is collected in this study. See Section 11 for further information on the collection of AEs and safety information.

9.13 Recording Data

The PI/ Sub investigator must ensure accuracy, completeness and timeliness of the data reported in the case report forms (CRFs) and in all other required reports. Source documentation is defined as the first-time data appear, and may include original documents, data, and records.

Subject questionnaires (e.g. DQ-39, EQ-5D-5L, MDS-UPDRS II ("best" and "worst" conditions), patient preference, patient satisfaction), physician assessments (e.g. GIC, MDS-UPDRS III and IV, UDysRS) and medication diary (When PD medication cycle data collected from an iPhone is missing, and the data recorded in a medication diary is used as the data) may be collected on paper forms, the paper forms of the questionnaires and/ or the medication diary will be retained at the site as the original source documentation.

Data reported on the CRFs, which are derived from the source documents, must be consistent with the source documents and discrepancies need to be justified with documented rationale, and approved by the PI or delegate. The PI/ Sub investigator must ensure the availability of source documents from which the information on the CRFs was derived. Where printouts of medical records are provided as source documents, those should be certified. Certification must contain (1) the signature of the individual making the copy, and (2) the date the copy was made.

The source documents must be made available for monitoring or auditing.

See Section 14.3 for data management in this study.

Refer to the following appendices for the questionnaire. (EQ-5D-5L (Appendix A), PDQ-39 (Appendix B), UDysRS (Appendix C), MDS-UPDRS II, III, IV (Appendix D), DBS GIC (Appendix E), Patient preference questionnaire (Appendix F), Patient satisfaction questionnaire (Appendix G).

Refer to Appendix H for the case report form (Sample collection item list).

